### VIII. Risks

### VIII.1 What are the risks to subjects including

- emotional or psychological
- financial
- legal or social
- physical?

### Physical risks:

Fasting for 8 hours: The most common risk when fasting is dehydration, therefore the subject will be encouraged to drink plenty of water. Subjects may experience hunger and irritability and if they experience fainting, nausea, or vomiting they will be instructed to stop fasting.

Blood sample: Potential risks associated with obtaining blood samples are minimal but include slight bruising, pain, a temporary feeling of faintness, and/or a small risk of infection. All blood draws will be performed by a research team member trained and certified in drawing blood or a nurse. There are no known risks associated with urine collection.

Endothelial cell collection. The risks related to the venous endothelial cell collection do not appear to be any greater than to those of placement of an intravenous catheter into antecubital vein. In the PIs experience with this technique at the University of Colorado Clinical and Translational Research Center, there were no adverse events encountered in >150 of these procedures performed between 2005-2009 in young, middle-aged and older healthy adults (17, 19, 52).

Pulse wave velocity: There are no known or foreseeable risks associated with the use of applanation tonometry for pulse wave analysis. ECG electrodes may cause minor irritation to the skin.

Carotid artery compliance and transcranial doppler of MCA via ultrasound. There are no known or foreseeable risks associated with the use of carotid and transcranial doppler echocardiography. ECG electrodes may cause minor irritation to the skin.

Brachial artery flow-mediated dilation (FMD): There is a risk of mild discomfort on the forearm when the blood pressure cuff is inflated and a mild temporary sensation of "pins and needles" in forearm and hand. This feeling is completely reversed within several minutes after the cuff is released with no permanent discomfort.

Cerebral artery blood flow velocity: There are no known risks associated with the use transcranial Doppler ultrasound of the middle cerebral artery.

Risks of breathing 2%, 4% and 6% carbon dioxide: Breathing in low concentrations of carbon dioxide at 2-4% for short period of time may be associated with possible symptoms such as drowsiness, rapid breathing, rapid heart rate or reduced hearing. At 6% carbon dioxide, this may be associated with headache, dizziness or shortness of breath, and feelings of being anxious. If these symptoms occur, they are reversed quickly upon breathing room air.

Forearm blood flow test: There is a risk of mild discomfort on the forearm and wrist when the blood pressure cuffs are inflated. This feeling is completely reversed within several minutes after the cuff is released with no permanent discomfort. There is a small risk of lightheaded or fainting in response to local lidocaine. There is a small risk of bruising at the sight of needle insertion a very small risk of permanent nerve damage or damage to the artery.

Microneurography: Approximately 7% of subjects experience minor tingling in the leg, foot or arm for a few days after the study, but these symptoms have been transient.

Retinal (eye) assessment: The flashes produced by the retinal imagining can be bright and the aftereffects can last several minutes at most.

Risks of drugs to be used in the study.

Salsalate. The most common side effects from the Salsalate medication include (in order of decreasing frequency) tinnitus ('rininging in the ears'), nausea, mild hearing impairment, rash, and vertigo in two studies with combined 280 subjects (percentages not available). Another study of 782 patients with osteoarthritis or rheumatoid arthritis were treated with about 3000 mg/day for 3 weeks, 324 (41%) experience one or more side effects with 234 (30%) requiring discontinuation of Salsalate for GI side effects (13.2%), tinnitus (6.7%), dizziness (1.7%) and 8.5% for other reasons.

Several small trials and one large multicenter clinical trial have been conducted using Salsalate in the dose and duration similar to the proposed dose and duration in this study. In one study of 20 obese middle-aged adults treated for 4 weeks with 4 g/day of Salsalate, 3 subjects required dose reduction of 500 mg due to tinnitus, headache, or dizziness(35). Subjects subsequently had stepped reductions of 500 mg titrated to maximal tolerable dose without symptoms, two tolerated 3.5 g/day and the other tolerated 3.0 g/day and both subjects completed the study. Mean serum salicylate concentrations at 4 weeks were 17.1 mg/dl (in therapeutic range 10-30 mg/dl). Three subjects were withdrawn from the study due to rash, but none had changes in serum measures of renal, electrolytes, anion gap or liver function.

In a 2nd study comparing 4.5 g/day to 3.0 g/day for 2 weeks in patients with Type 2 diabetes, 6 of 7 subjects receiving 4.5 g/day experienced tinnitus but symptoms resolved with dose reduction (45). Serum salicylate concentrations were 28.4 and 19.0 mg/dl at 1 and 2 weeks respectively. At 3.0 g/day, no subjects experience tinnitus or any side effects, but serum salicylate concentrations were in the subtherapeutic range (5.4 mg/dl) based on rheumatologic standards. In that same study, another 17 diabetic patients were randomly assigned to the maximal tolerable dose of 3-4 g/day for 4 weeks. Three of the 8 subjects randomized to 4 g/day, developed tinnitus but symptoms resolved with reduction of dose to 3.5 g/day for remainder of study (45). Serum salicylate concentration was 13.3 mg/dl after 4 weeks and there was no change in serum creatinine or anion gap.

A recent multicenter trial (Golfine A, et al., Ann Intern Med 2010) Targeting Inflammation Using Salsalate in Type 2 Diabetes (TINSAL-T2D; NCT00392678), 108 patients with type 2 diabetes were randomly assigned to placebo, 3.0, 3.5, or 4.0 g/day for 14 weeks with the primary endpoint being reduction in HbA1c (83). In this longer duration study (compared to our study), about 19-22% of subjects reported tinnitus, one with baseline tinnitus withdrew and 3 patients required dosage reduction but who completed the study. Although there were no serious adverse events, 22-30% of patients experienced hypoglycemia. However, these patients were also receiving concurrent anti-glycemic sulfonylurea therapy for glycemic control. There was also a small trend for an increase in urinary albumin and the 3.5 g/day group showed a small increase in serum creatinine concentration, but no changes in liver function or anion gap. Mild GI symptoms (heartburn, nausea, vomiting, diarrhea) were slightly more common in Salsalate than placebo groups, but there was no episodes of GI bleeding and no subjects required reductions in Salsalate dose. A follow-up multicenter trial (TINSAL-T2D II) is currently underway investigsting the effects to 3.5 g/day of Salsalate on HbA1c for 1 year in patients with type 2 diabetes (NCT00799643). Lastly, in previous study by the PI using high dose Salsalate (4.5 q/day) for 4 days in healthy obese middle-aged/older adults, 2 out of the 17 subjects during the Salsalate treatment withdrew from the study due to dizziness (n=1) and tinnitus (n=1), but neither subject had serum concentrations in the toxic range (19).

Metabolic acidosis: There is a very small risk of metabolic acidosis from salicylate toxicity although none of the above clinical trials above reported any incidence of this. This usually can be treated by stopping salsalate medication and with IV fluid and electrolyte therapy.

Heart attack or stroke: Because Salsalate is an NSAID, people who take NSAIDs (other than aspirin) may have a higher risk of having a heart attack or a stroke than people who do not take these medications. These events may happen without warning and may cause death. This risk may be higher for people who take NSAIDs for a long time and in those who have cardiovascular disease. There is no reported increased risk of heart attack or stroke in individuals on Salsalate so it cannot be determined what the exact risk (if any) is f Salsalate at the dose and duration in this study. Subjects are instructed to get emergency medical help right away if they experience any of the following symptoms during the study: chest pain, shortness of breath, weakness in one part or side of the body, or slurred speech.

Gastrointestinal bleeding: NSAIDs such as salsalate may cause ulcers, bleeding, or holes in the stomach or intestine. These problems may develop at any time during treatment, may happen without warning symptoms, and may cause death. The risk may be higher for people who take NSAIDs for a long time, are older in age, have poor health, smoke, or drink large amounts of alcohol or are on the following medications: anticoagulants ('blood thinners') such as warfarin (Coumadin); aspirin; other NSAIDS such as ibuprofen (Advil, Motrin) and naproxen (Aleve, Naprosyn); or oral steroids such as dexamethasone (Decadron, Dexone), methylprednisolone (Medrol), and prednisone (Deltasone). Also tell the research team if you have or have ever had ulcers, bleeding in your stomach or intestines, or other bleeding disorders. All of these medication are exclusion criteria in our study. Subjects are instructed to stop taking salsalate and call the study doctor if they experience any of the following during the study: severe stomach pain or heartburn, vomiting a substance that is bloody or looks like coffee grounds, blood in the stool, or black and tarry stools.

Risk of Reye's syndrome: If the subject has a recent history of a viral infection such as chickenpox or influenza they will not be allowed to participate because of the risk of developing Reye's syndrome (potentially fatal disease associated with viral illness and salicylate/aspirin use). If he subject has had recent flu-like symptoms you will be required to wait 2 weeks without any flu symptoms before participating.

Forearm blood flow test drugs:

o Acetylcholine, Sodium nitroprusside, and Vitamin C. These drugs will be infused into the brachial artery and will cause changes only in the blood flow in the forearm. Because the doses used are very small, there should be little or no effect on systemic hemodynamics (e.g., blood pressure and heart rate).

o Lidocaine: 1% lidocaine will be used to numb the area on the arm for insertion of the brachial artery needle. Likely and expected effects include mild, temporary burning at the site of injection and a sensation of coolness or numbness at the site of the injection. Unlikely, but possible reactions include lightheadedness, dizziness, ringing in the ears, nervousness, and blurred vision. Individuals known to be allergic to anesthetics like lidocaine (e.g., novocaine- used for tooth fillings) should notify the investigator before participating and will not undergo the forearm blood flow test.

Brachial artery FMD test drugs.

o Sublingual (under the tongue) nitroglycerin tablet: Nitroglycerin tablet may cause transient low blood pressure, dizziness, flushing, and headache but should only last for 5-10 minutes. If subject feels any of these symptoms we will keep him/her lying down until the symptoms pass and blood pressure is back to normal.

Psychological risks: The study only enrolls healthy subjects without psychiatric diagnoses and there are no foreseeable psychological risks with this study.

Social Risks: There are no foreseeable social risks with this study

Legal Risks: There are no foreseeable legal risks with this study.

Confidentiality and financial risks: Subjects are at risk of breach of their confidentiality. All research team members have undergone confidentiality training, and are aware of potential consequences for breach of confidentiality. This will minimize this risk. Other than the cost of transportation there is no forseeable financial risk with this study.

### VIII.2 What have you done to minimize the risks?

- If applicable to this study ALSO include:
  - How you (members of your research team at Iowa) will monitor the safety of individual subjects.
  - Include a description of the availability of medical or psychological resources that subjects might require as a consequence of participating in this research and how referral will occur if necessary (e.g. availability of emergency medical care, psychological counseling, etc.)

### Plan for Monitoring for Risks:

During the study if the subject experiences any mild but tolerable expected side effects such as tinnitus, dizziness, nausea, headache, they will be asked to keep a log of these including the date, the duration, and the severity by rating on a scale of 1 (mild) to 10 (severe/intolerable). If the subject feels the side effects are uncomfortable or intolerable, then they will be instructed to call in to the Research Nurse during business hours. If after business hours, weekends, or holiday, the subject will be instructed to call in the UIHC access number and ask for [name] to be paged. The Research Nurse or [name] (although he will be blinded) will instruct the subject to skip the next dose and if the symptoms/side effects have resolved at time of next dose (in 12 hours), they will be instructed to take the next dose at 500 mg less and continue at that dose. [name] will call/page [name] for

consultation if necessary and [name] will serve as back up if [name] is out of town or unavailable. If [name] is out of town or unavailable then [name], MD will be available to consult. If symptoms do not resolve or worsen at time of next scheduled dose, the subject will be instructed to not take that dose, and to come to the CRU to have a blood sample to assess serum salicylate concentrations. If side effects that are life threatening, the subject will be instructed to call 911. If serum salicylate concentrations are not in the toxic range (<30 mg/dl), the subject will be will be re-assessed in 12 hours to confirm that salicylate concentrations are decreasing and symptoms resolved. If symptoms resolve, the subject can take next am or pm dose at 500 mg lower or be withdrawn from the study as recommended by [name].

If blood plasma salicylate concentrations are in the toxic range (>30 mg/dl), the subject will be withdrawn from the study and [name] and [name] notified. Serum electrolytes (including anion gap), urinalysis and respirations may be obtained in the case of suspected metabolic acidosis due to Salsalate toxicity. If metabolic acidosis is suspected, then [name] will be notified and determine appropriate medical management in the CRU or referral to the UIHC Emergency Department.

Scheduled safety visit. Subjects will come in at 2 weeks for Visit 5 (approximately Day 14 depending on scheduling) and to have serum salicylate concentrations measured and to confirm no toxicity. The Research Coordinator/Nurse or research staff will review their 2 week side effect log (see attached survey) and survey subjects for any symptoms/side effects and. Subjects will also have serum salicylate concentrations measured at experimental visits 6 and 7.

- VIII.3 Does this study have a plan to have an individual or committee review combined data from all subjects on a periodic basis (such as summary or aggregate safety and/or efficacy data)?

  Yes
  - VIII.4 Describe the plan to review combined data from all subjects, such as summary or aggregate safety and/or efficacy data. Include the following:
    - Describe what data will be summarized and reviewed
    - Describe how frequently data will be reviewed.

The Data Safety Monitoring Plan will consist of a bi-annual independent review of the protocol by [name], Department of Internal Medicine, Division of Nephrology. The PI will provide a bi-annual report to the [name] summarizing the following:

- a) Data on progress of the protocol including subject recruitment, attrition, and minority involvement. Reasons for attrition or other recruiting issues
- b) Data on safety of research participants including unblinded data of serum salicylate, creatinine, ALT/AST concentrations at baseline and from safety visits, data on reasons for any dosing reductions in Salsalate that occurred, and data collected from evening telephone questionnaires for subject symptoms;
- c) Data on compliance in reporting of any adverse events
- d) Data on protocol compliance and any amendments to the protocol
- e) Data on any safety issues that occurred during the 6 month period.
- f) He will confirm that any action that results in the temporary or permanent suspension of the protocol is reported to all the appropriate monitoring bodies such as the CRR protocol committee, IRB, FDA, NIH, or other sponsor, etc.

Every 12 months, the PI will summarize outcome data and provide to [name] for review of the efficacy of treatment intervention on primary outcomes

VIII.5 Will overall safety monitoring be performed by individual(s)/committee at The University of Iowa. (NOTE: If this study involves more than

minimal risk, in most cases these should be individuals who are not members of the study research team.)?

Yes

VIII.6 List names:

[name]

VIII.7 Will overall safety monitoring be performed by individuals or committee not associated with The University of Iowa (such as a study Data Safety Monitoring Board)?

No

IX. Benefits

IX.1 What are the direct benefits to the subject (do not include compensation or hypothesized results)?

There may be no direct benefits to the subject, but subject may experience lowering of fasting blood glucose, triglycerides, HbA1C and blood pressure

IX.2 What are the potential benefits to society in terms of knowledge to be gained as a result of this project?

The potential benefits to society include determining if a commonly used antiinflammatory drug used to treat chronic inflammatory diseases such as rheumatoid arthritis, will be effective for improving cardiovascular function in obese adults with prediabetes. This could have favorable clinical implications for older adults in possibly reducing risk of cardiovascular diseases most notably atherosclerosis.

X. Privacy & Confidentiality

X.1 What are you doing to protect the privacy interests of the subjects?

The minimum amount of data necessary to complete the aims will be collected during the study. The informed consent process will be conducted in a private exam room in the CRU with the door closed. During screening and experimental procedures will be conducted in private exam rooms in the CRU with the door closed. Only personnel directly involved in the study will be allowed in the rooms.

X.2 Are you collecting the Social Security Number of any subjects for any purpose?

Yes

X.3 Provide the intended usage of SSN:

• To provide compensation to subjects

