for measurements of forearm blood flow using venous occlusion plethysmography c. A physician trained in brachial artery catheterization in the Human Cardiovascular Research Lab will then perform brachial artery catheterization with 27 G needle and undergo incremental infusions of saline, acetylcholine, acetylcholine + vitamin C (ascorbic acid), and sodium nitroprusside + vitamin C (see Expermental Procedures for details)

- d. Subject will be escorted to Dept of Ophthalmology in Pomerantz Bldg and have picture of retinal performed (scan takes  $\sim$ 10 min)
- e. Subject will be given snack or lunch in CRU.
- f. Subjects will be randomized in a 2:1 scheme to Salsalate or placebo
- g. Nurse will dispense 35 day supply (210 tablets) of Salsalate (dose 3000 mg/day = 500 mg tablets x  $6/\text{day} \times 35 \text{ days} = 210 \text{ tablets}$ ) or placebo
- h. Subject will take first dose of Salsalate (500 mg x 3 pills) or placebo at CRU and 2nd dose (1500 mg) at home in evening- this is Day 0

Visit 5 (45 min) ~Day 14: Subject will return to CRU for venous blood sample to measure serum salicylate (4.5 ml x 2 PST tubes: total 9 ml or ~0.5 tablespoons), Blood pressure, HR and survey of any side effects. If any side-effects/symptoms present, nurse coordinator will follow instructions as outlined in section VIII.2 "Plan for Managing Risks". Subject will receive 3-day food record booklet from CRU bionutritionist

Days 25: Coordinator or research staff will call subject in the evening to remind subject to start 3-day dietary record on days 26, 27, 28.

Visit 6 (5 hours) Betwee Day 26-34: Post-experimental visit #1 (FMD, PWV and Retina)

- a. Subject will take morning dose of Salsalate/placebo and return to CRU between Day 26 -35 for venous blood sample to measure serum salicylate, blood pressure, HR; and survey of any side effects
- b. All vascular measurements of Visit 3 will be repeated
- c. Middle cerebral artery blood flow velocity using transcranial dopper during the following protocol to measure cerebral vasoreactivity to hypercapnia:
- -After 3 min of normal breathing, subjects will perform 2, 30 second breathholds sparated by 3 min.
- -Next, After 3 min of room air breathing, 3 min of breathin 2%CO2, 3 min of breathing 4%CO2 (balanced with 21%O2 and N) will be performed followed by 3 min of room air

breathing.

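### VIII.1 tells subjects to stop salsalate for severe stomach pain or heartburn and for GI bleeding signs; VIII.2, which staff follow, neither repeats nor excepts this, and its default is to skip one dose and resume lower

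*Combined protocol and SAP*

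**What the plan says.** Section VIII.1, in its paragraph on gastrointestinal bleeding, says that NSAID-related ulcers, bleeding or perforation "may happen without warning symptoms, and may cause death". It then gives a subject-level rule: "Subjects are instructed to stop taking salsalate and call the study doctor if they experience any of the following during the study". The triggers are "severe stomach pain or heartburn, vomiting a substance that is bloody or looks like coffee grounds, blood in the stool, or black and tarry stools". Nothing is said about restarting, or about whether the stop is temporary or permanent.

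Section VIII.2, Plan for Monitoring for Risks, opens with "any mild but tolerable expected side effects such as tinnitus, dizziness, nausea, headache", which the subject records in a log. The next step begins "If the subject feels the side effects are uncomfortable or intolerable": the subject then calls the research nurse, or a paged clinician out of hours. The person answering will "instruct the subject to skip the next dose and if the symptoms/side effects have resolved at time of next dose (in 12 hours"; if they have, the subject takes the next dose at 500 mg less and stays at that level. If symptoms have not resolved or are worse, the dose is withheld and serum salicylate is measured. With a level outside the toxic range and symptoms that then resolve, the subject either resumes 500 mg lower or is withdrawn on a clinician's recommendation. Life-threatening effects lead to a 911 call, and a salicylate level above 30 mg/dl leads to withdrawal.

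Section VII.E.6 connects the two. If a subject reports any side effect or symptom at Visit 5, the "nurse coordinator will follow instructions as outlined in section VIII.2". No symptom is excepted.

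**The concern.** VIII.1 tells the subject what to do, and VIII.2 tells staff how to answer when the subject calls or attends. For the listed gastrointestinal signs, both apply to the same contact. A subject who has stopped the drug as VIII.1 instructs, and whose severe heartburn has eased by the next dose, would be told under the VIII.2 default to start again at a lower dose.

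Safety comes first, because the document itself describes the underlying events as potentially fatal. There is also a consequence for the data. Whether such a subject is off drug, on a reduced dose or withdrawn depends on which section the staff member reads. That affects exposure, and possibly completeness of outcomes, in a trial planned with 20 salsalate and 10 placebo subjects.

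**Working it through.** The check is a comparison of text; no stated figure is involved.

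| Event | VIII.1 | VIII.2 |
|---|---|---|
| Tinnitus, dizziness, nausea, headache | Described as side effects; no instruction to stop | Log if tolerable; otherwise skip a dose and resume 500 mg lower if resolved |
| Severe stomach pain or heartburn | Stop and call the study doctor | Not named; meets the uncomfortable-or-intolerable trigger, so skip and resume if resolved |
| Blood in vomit or stool, tarry stools, not judged life threatening | Stop and call the study doctor | Not named; no branch of its own |
| Life-threatening effect | Not at issue here | Call 911 |

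1. **Does VIII.2 carry the VIII.1 rule over?** No. It mentions neither severe stomach pain, heartburn nor bleeding, and does not refer back to VIII.1.

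2. **Does VIII.2 exclude these symptoms from its default?** No. Its opening examples are an open list. Heartburn can be read into it, because VIII.1's account of the multicentre type 2 diabetes trial counts heartburn among mild gastrointestinal symptoms seen slightly more often on salsalate. The same symptom, when severe, is a stop symptom two paragraphs later.

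3. **Are staff sent to VIII.2 for these symptoms?** Yes, at Visit 5, without exception. VIII.2 is also the text that governs telephone calls.

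4. **Are the two actions the same?** Not as written. VIII.1 has a stop with no restart. VIII.2 has one skipped dose, then a restart that depends on symptoms having resolved. That restart test also sits uneasily with VIII.1's statement that these problems can arise without warning symptoms.

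5. **Does another text settle it?** None that the document points to. VII.B.11 says there is no separate written protocol.

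6. **Scale per subject.** One subject handled differently is 1/20 = 5% of the planned salsalate arm, or 1/10 = 10% of the placebo arm. This is a weight per event and says nothing about how many events to expect.

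**The case against.** The best defence is that a specific rule governs over a general one. VIII.1 deals with named warning signs, while VIII.2 opens with mild, expected effects, and its next sentence refers back to that class. VIII.1 does not call the stop permanent, so holding the drug and calling is compatible with skipping a dose. VIII.2 also provides for physician consultation, a 911 branch and, after unresolved symptoms and a salicylate check, a withdrawal option. The consent pages and the side-effect log are not available here and may say more.

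Much of this stands, and it limits the point. A reader might infer that VIII.2 orders a subject with overt bleeding to skip one dose and resume. The text does not say that. For bleeding signs the problem is an unreconciled gap, not an express order. For severe heartburn or stomach pain the defence is weaker: these fit the VIII.2 trigger directly, and Visit 5 sends every symptom there. Consultation is only as necessary, and the withdrawal option is reached only if symptoms have not cleared at the first step.

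Three further inferences are tempting but unsupported:

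- **Rash.** In a cited 4-week study at 4 g/day, "Three subjects were withdrawn from the study due to rash". That is what another study did at a higher dose. This protocol sets no rash rule for VIII.2 to contradict.
- **Frequency.** The 13.2% of 782 arthritis patients who discontinued for gastrointestinal effects covers all such effects, not the listed signs. The 108-patient diabetes trial reported no gastrointestinal bleeding, and section VI.13 excludes ulcer history, bleeding disorders, dyspepsia, severe reflux, anticoagulants and concomitant NSAIDs. Applying 13.2% to 20 subjects would not estimate the disputed events.
- **Persistent symptoms at a non-toxic level.** VIII.2 gives no final outcome for this case. That is a separate missing detail and not part of this conflict.

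**Conclusion.** The point holds in a limited form. Severe stomach pain or heartburn falls under two instructions that differ: stop and call in VIII.1, skip and resume lower if resolved in VIII.2. The listed bleeding signs, when not judged life threatening, have a stop instruction in VIII.1 and no branch of their own in VIII.2. Because Visit 5 sends every symptom to VIII.2, this is a conflict between stated safety rules, not only missing detail, and it should be resolved.

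The size cannot be stated as a number of subjects. The conclusion rests on two assumptions: that staff apply VIII.2 as written, and that the consent form and side-effect log, which were not available, do not already resolve it.

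**What to change.** Reconcile the Visit 5 text in VII.E.6, the gastrointestinal paragraph in VIII.1 and the plan in VIII.2:

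- List the VIII.1 gastrointestinal symptoms in VIII.2 as a separate branch from the tinnitus, dizziness, nausea and headache pathway.
- State one action for them, in the same terms in both sections, including whether a stop is temporary or permanent and who decides.
- Refer Visit 5 staff and those answering telephone calls to that branch.
- Check that the consent form and side-effect log agree.

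Which action applies is for the sponsor's physicians to decide. The cost is an amendment to the wording and to staff instructions, with no added visit or procedure. Depending on how it is resolved, slightly more or fewer subjects may come off drug.
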